### **13.3.3 Pain intensity recording in the electronic diary**

Analysis and display of average pain recorded in the electronic diary is described in Section 13.1.1). Derivation and analysis of worst and current pain intensities recorded in the electronic diary will be done in the same manner.

### **13.3.4 Active range of motion (AROM)**

For a detailed description of the AROM please see protocol Section 12.3.5.

For subjects having decreased AROM at baseline (diagnosed based on clinical judgment; sign “Motor abnormalities” ticked “yes”, sub-category “decreased AROM” ticked “yes” on the CRPS Severity Score at baseline), both affected and unaffected limbs will be measured.

The AROM in each of the unaffected and affected limbs will be measured 2 times, the AROM consists of two components flexion and extension, the sum of both builds the AROM. The results of both measurements and both components will be documented; only the best performance of the 2 repetitions will be used for further analysis, i.e. the highest flexion and the highest extension value per limb will be added and used further.

The ratio of the AROM of the affected and the unaffected (denominator) limb will be calculated.

Descriptive summaries including changes from baseline will be generated for the AROM of the affected and the unaffected limb and the ratio of the two. The summaries will distinguish between

the CRPS locations and display results for upper extremity and lower extremity as well as left and right body site separately.

### **13.3.5 CRPS Severity Score**

The signs and symptoms of CRPS are recorded using tablet computers. The investigator examines the signs. The subject reports his/her symptoms with a recall period of 48 hours. At the Enrollment Visit, patients record their symptoms with recall period since onset of CRPS.

To derive the CRPS severity score, the symptoms reported with recall period 48 hours will be used.

Subjects will be queried on 8 self-reported symptoms (queried YES or NO):

1. continuing, disproportionate pain;
2. allodynia and/or hyperalgesia;
3. temperature asymmetry;
4. skin color asymmetry;
5. sweating asymmetry;
6. edema;
7. dystrophic changes;
8. motor abnormalities.

Moreover, subjects will be examined for 8 signs (observed on examination, queried YES or NO):

1. hyperalgesia to pinprick;
2. allodynia;
3. temperature asymmetry by palpation;
4. skin color asymmetry;
5. asymmetric edema;
6. sweating asymmetry;
7. dystrophic changes; and
8. motor abnormalities.

Each sign or symptom is assigned a dichotomous value (1 = presence; 0 = absence). The resulting CRPS severity score ranges from 0 to 16, with higher scores indicating greater CRPS severity. If one of the 16 signs and symptoms is missing the CRPS severity score will not be calculated and is considered missing.

A descriptive summary will be created by sign/symptom and visit (recall period 48 hours),

A graphical display over the entire trial will be created for the proportion of subjects with a sign/symptom, for each of the signs and symptoms, all treatments will be presented in one plot.

Furthermore, a descriptive summary of the continuous CRPS severity score and the corresponding change from baseline will be generated. A graphical plot of the means and 95% CI of the CRPS severity score over time will be created. All treatments will be presented in one plot. Assessments at visit 2 are considered baseline assessments.

### **13.3.6 Patient Global Impression of Change (PGIC)**

The observed values of the PGIC will be summarized descriptively (categorical). Furthermore, the following categories will be pooled and presented:

- ‘very much improved’ and ‘much improved’
- ‘much worse’ and ‘very much worse’
- ‘very much improved’ and ‘much improved’ and ‘minimally improved’.
- ‘no change’ and ‘minimally worse’ and ‘much worse’ and ‘very much worse’

### **13.3.7 Patient Global Impression of Severity (PGI-S).**

The observed values of the PGI-S will be summarized descriptively (categorical) and shift tables with regards to the baseline assessment will be generated. In addition, a shift table between Week 52 and Week 26 will be produced.

### **13.3.8 EuroQoL-5 Dimension-5 level (EQ-5D-5L)**

The EQ-5D-5L has 5 dimensions: mobility, self-care, usual activities, pain/discomfort, and anxiety/depression. Each of the 5 dimensions has 5 possible levels: no problems, slight problems, moderate problems, severe problems, and extreme problems.

The health state of the subject is coded by the vector of the reported levels in each of the 5 dimensions. An EQ-5D-5L Health Status Index will be derived from the 5-dimensional health status vector using a lookup table that can be downloaded from the website of the EuroQol group. The index set provided for the US in the spread sheet “EQ-5D-5L value sets” of the Excel file “EQ-5D-5L\_Crosswalk\_Value\_Sets.xls” will be used to assign an index value to the health status vector of a subject. For the US general population, the possible EQ-5D-5L index scores range from -0.109 for the health status vector “55555” to 1.0 for the vector “11111” on a scale where an index value of 0.0 represents death and 1.0 represents perfect health.

The EQ-VAS ranges from 0 (worst imaginable health) to 100 (best imaginable health).

A descriptive summary of the 5 categorical EQ-5D-5L dimensions will be generated by dimension, and visit. Furthermore, a descriptive summary of the continuous EQ-5D-5L index and the EQ VAS, and the corresponding changes from baseline will be generated by visit. In addition, for Week 52 the change to Week 26 will be generated.

### **13.3.9 PROMIS-29 profile and PROMIS-EDDEP39**

The Patient-Reported Outcomes Measurement Information System (PROMIS-29®) profile assesses 7 domains, i.e., depression, anxiety, physical function, pain interference, fatigue, sleep disturbance, and ability to participate in social roles and activities, each with 4 questions and a recall period of 7 days (Cella et al. 2007).

In addition, suicidal ideation will be assessed using the PROMIS-EDDEP39, which is Question EDDEP39 of the PROMIS Item Bank version 1.0 – Emotional Distress – Depression (Pilkonis et al. 2011).

The following description can be found in the PROMIS – Adult Profile Instruments (2015).

Each question has five response options ranging in value from 1 to 5, except for the Pain Intensity item (Question number 29 [GLOBAL07]) which has eleven response options ranging in value from

---

0 to 10. A raw score is created from each domain that makes up the Profile. To find the total raw score for a domain with all questions answered, the values of the response to each question within the domain is summed up. For example, for the 29-item Profile, the lowest possible raw score within Anxiety is 4 (a score of 1 on all four items); the highest possible raw score is 20 (see all short form scoring tables in Appendix).

Descriptive summaries including changes from baseline for the domains will be generated. Question number 29 (GLOBAL07) will be descriptively summarized and changes from baseline will be calculated for Week 16 and Week 22 only

The Question EDDEP39 of the PROMIS Item Bank version 1.0 – Emotional Distress – Depression (PROMIS-EDDEP39) will be descriptively summarized. A shift table will be generated to display changes from baseline.

### **13.3.10 Short-Form McGill Pain Questionnaire 2 (SF-MPQ-2) - 6 neuropathic items**

The SF-MPQ-2 is a single measure of the major symptoms of both neuropathic and non-neuropathic pain. The pain qualities will be assessed using the 6 neuropathic items from the SF-MPQ-2. A total score for the neuropathic subscale will be calculated as a mean of all 6 neuropathic items (Gauthier et al. 2014).

Subjects will be asked to consider and report only the pain related to the CRPS when completing the instrument using the tablet computers maintained at the sites.

Descriptive summaries including changes from baseline will be generated for the neuropathic total score as well as for each of the 6 individual items.

### **13.3.11 Pain Catastrophizing Scale (PCS)**

The PCS will be used as a measurement tool to capture pain catastrophizing; the scale will be completed by the subjects using the tablet computers.

Derivation and details on the analysis of the PCS is described in detail in the User Manual of the PCS (Sullivan et al. 2009). The PCS is a 13-item instrument asking subjects to indicate the degree to which they experienced each of 13 thoughts or feelings when experiencing pain, on 5-point scales with the end points (0) not at all and (4) all the time. The PCS yields a total score. The PCS total score is computed by summing responses to all 13 items and ranges from 0 – 52.

Descriptive summaries including changes from baseline will be generated for the total score.

### **13.3.12 Pain Self Efficacy Questionnaire (PSEQ).**

Ten items were selected to reflect a wide variety of classes of activities and tasks. Respondents consider how confident they are performing each activity, while taking their pain into account. Each activity is rated by selecting a number on a 7-point scale, where 0 equals “not at all confident” and 6 equals “completely confident”. A total score is calculated by summing the scores for each of the 10 activities, yielding a maximum possible score of 60. Higher scores reflect stronger self-efficacy beliefs (Nicholas 2007). The Total Score will be displayed by descriptive summaries including changes from baseline.

## **13.4 Health economic and work productivity data**

### **13.4.1 Work Productivity and Activity Impairment Questionnaire: CRPS (WPAI: CRPS). (US sites only)**

History of CRPS including impairments of personal activities, both work-related (e.g., absenteeism/presenteeism) and non-work-related will be captured using the WPAI: CRPS.

Descriptive summaries will be generated for all questions and displayed by treatment and week.

### **13.4.2 Medical resources utilization. (US sites only)**

Medical resource utilization and health economics data will include information regarding hospitalization, emergency room visits, nursing home stays, health care provider (other than trial investigator) contacts, home services, home help, and special devices used due to CRPS-related symptoms and pain.

The responses to the questions will be documented on paper and stored as part of the source data. Data will be transcribed into the eCRF by the investigator or delegated site staff.

Descriptive summaries will be generated by treatment and visit.

Parameters summarized are:

- Healthcare Utilization domain (No, Yes):
  - Hospitalization during past 12 weeks (if yes, number of times).
  - Emergency room treatment (no hospitalization) (if yes, number of times).
  - Nursing Home Stay (if yes, number of nights).
  - Health Care providers (multiple answers possible) (if yes, number of visits and number of phone calls).
- Home Service, Home Help, Formal and Informal Caregiving, Devices
  - Home Services and Help (multiple answers possible) (if yes, number of times and average duration (min))
    - Cleaning services.
    - Meals delivered.
    - Formal childcare assistance.
    - Transportation.
    - Caregiving.
  - Special Product/Device/Tool
    - Special equipment/assistive tools.

## **14 ANALYSIS OF PHARMACOGENETIC DATA, OMICS DATA AND PHARMACOKINETIC AND PHARMACODYNAMIC PARAMETERS**

All measurements and analyses of pharmacogenetics data and omics data will be described in separate analysis plans.

All measurements and analyses of pharmacokinetic and pharmacodynamic parameters will be described in separate pharmacometric analysis plans.

### **14.1 Analysis of plasma concentration**

In this trial, plasma concentrations of the following analytes will be investigated: the parent compound neridronic acid. Analysis will be performed on the PKS.

Plasma concentration data will be displayed with descriptive statistics including the coefficient of variation, the geometric mean and geometric coefficient of variation as defined in Section 19.1.5 at each scheduled time point and for each analyte. Missing data will be shown as a separate category in the summary tables. The individual data will be displayed in the subject data listings.

Descriptive statistics of the concentrations will only be determined if at least 75% of the observations at a given sampling point have quantifiable results which have not to be excluded due to the deviation rules. Data excluded from the descriptive statistics will be shown in brackets (e.g., like [ $<$ LLOQ] or with the measured value like [32.3]) in the respective listings.

Missing data will be treated as such and will not be imputed or replaced in any way if not specified otherwise.

### **14.2 Bone turnover markers and markers for disease severity or CRPS progression**

Bone turnover markers will be analyzed in the PDS. Soluble interleukin-2 receptor (sIL-2R) will be analyzed in the SAF.

The following bone turnover markers are assessed:

- Bone formation markers:
  - Procollagen type I amino-terminal propeptide (PINP).
  - Bone alkaline phosphatase (BAP).
- Bone resorption marker:
  - C-terminal telopeptide of type I collagen (CTX).

All bone turnover marker data will be listed in a subject data listing.

Bone turnover marker values as well as sIL-2R values, including changes from baseline, will be descriptively summarized by parameter and time point. Baseline is defined by the value on Day 1 (Visit 2).

For bone turnover markers as well as sIL-2R values a graphical plot of the mean and 95% CI of bone turnover marker values over time will be presented. Similarly, a plot of the mean change from baseline of bone turnover marker values over time will be presented. Furthermore, a display by fasting and non-fasting status will be done as assessed on the 'Date of confirmed Visit' in the eCRF. The non-fasting status consists out of non-fasting, insufficient fasting and unknown categories.

All bone turnover marker data and sIL-2R data will be listed in a subject data listing.

## 15 SAFETY ANALYSES

No statistical tests for comparison of safety data between treatment groups will be performed.

Safety data will be summarized descriptively by treatment group and by visit if applicable.

All safety data will be presented for the SAF unless otherwise specified.

The interim integrated clinical trial report will report all safety data until the cut-off date (last subject performing its Visit 11 (Week 26)), regardless of whether data is assessed before or after Visit 11.

### 15.1 Adverse events

A treatment emergent adverse event (TEAE) is defined as any adverse event that based on start date and start time information occurs in the on-treatment-period as defined in Section 8.2.2.

A pre-treatment non-TEAE is an adverse event starting in the pre-treatment period as defined in Section 8.2.2.

If there are partial dates or times, an adverse event will be considered treatment emergent unless the information available will clearly exclude it. Further details can be found in Section 19.1.6.1.

Assignment of TEAEs to treatment will be based on the definition of the on-treatment-period given in Section 8.2.2, thus, TEAEs occurring during the on-treatment period are assigned to the respective treatment. TEAEs will be assigned to treatment based on their start date.

Display by trial phase refers to a display by:

- Treatment Period A/Follow-up Period 1.
- Treatment Period B/Follow-up Period 2.

For display by trial phase TEAEs starting in the Follow-Up Period 2 will be displayed within one of the four treatment groups according to their treatment schedule in Treatment Period A and B. Display for Treatment Period B/Follow-up Period 2 will in addition to the four treatment groups include a neridronic acid overall group combining all subjects that have received a dose of neridronic acid.

For adverse events where the intensity changes over time, the maximum intensity observed during the whole duration of the adverse event will be documented.

The causal relationship of TEAEs to IMP is categorized as follows:

Category	Assessment by investigator
Related	certain probable/likely possible
Not related	unlikely not related
Unknown	unassessable/unclassifiable conditional/unclassified causal relationship is missing

An adverse event is considered to be “expected” if it is one where the nature or intensity is consistent with the information in the neridronic acid investigator’s brochure. Otherwise it is considered to be an “unexpected” adverse event.

### 15.1.1 Adverse event summaries

The following overview tables will be generated by treatment group and overall and by trial phases as defined above.

#### 1. Summary of the number and percentage of subjects with at least 1

- TEAE.
- Serious TEAE.
- Non-serious TEAE.
- Unexpected TEAE.
- Related TEAE.
- Related serious TEAE.
- TEAE leading to discontinuation from IMP.
- TEAE leading to discontinuation from the trial.
- Death.

The percentage denominator will be the number of subjects.

#### 2. Summary of the number and percentage of TEAEs for:

- TEAEs.
- Serious TEAEs.
- Non-serious TEAEs.
- Unexpected TEAEs.
- Related TEAEs.
- Related serious TEAEs.
- TEAE leading to discontinuation from IMP.
- TEAE leading to discontinuation from the trial.
- Death.

The percentage denominator will be the total number of TEAEs.

### **15.1.2 Incidence, incidence rates and number of events**

The incidence of an adverse event is defined as the number of subjects with occurrence of this adverse event during the period of interest.

The incidence rate (crude incidence rate [CIR]) of an adverse event is defined as the number of subjects with occurrence of this adverse event during the period of interest divided by the total number of subjects N in the respective group (e.g., treatment group).

The incidence, incidence rate, the number of events, and the percentage of events will be summarized by PT (sorted by decreasing incidence rate in the neridronic acid treatment arm for:

- TEAEs.
- Serious TEAEs.
- Non-serious TEAEs.
- Related TEAEs.
- TEAEs associated with acute phase reactions.

Percentages will be calculated related to the total number of subjects/events presented in the respective table e.g., for the presentation of PTs for serious TEAEs percentages will be related to the number of subjects with serious TEAE/the total number of serious TEAEs, respectively.

Adverse events associated with acute phase reaction include the PT Acute Phase Reaction in all cases. They also include the PTs Arthralgia, Bone Pain, Chills, Fatigue, Headache, Influenza-Like Illness, Musculoskeletal Chest Pain, Musculoskeletal Pain, Myalgia, Pain, Pain In Extremity and Pyrexia, but only if occurring in the first 3 days after 1st IMP intake and not lasting longer than 3 days.

For serious TEAEs, percentages will additionally be presented related to the total number of all subjects/events, respectively.

The incidence, incidence rate, the number of events and the percentage of events will be summarized by SOC and PT (sorted alphabetically) for each:

- TEAEs.
- TEAEs with an incidence rate of at least 5% ( $\geq 5\%$ ) in any of the treatment groups.
- Serious TEAEs
  - Serious related TEAEs.
  - Serious fatal TEAEs.
  - Serious fatal related TEAEs.
- Non-serious TEAEs.
- Related TEAEs.

Percentages will be calculated related to the total number of subjects/events presented in the respective table e.g., for the presentation of SOC and PT for serious TEAEs percentages will be related to the number of subjects with serious TEAE/the total number of serious TEAEs, respectively.

For serious TEAEs, percentages will additionally be presented related to the total number of all subjects/events, respectively.

For all enrolled subjects, the incidence, incidence rate, the number of events and the percentage of events (related to the total number of events) will be summarized by SOC and PT (sorted alphabetically) for each:

- Pre-treatment non-TEAEs.
- Serious pre-treatment non-TEAEs.

Presentation will only be overall and not per treatment.

The number and percentage of events will be summarized by SOC and PT (sorted alphabetically) for the following TEAE descriptors:

- Intensity: mild, moderate, severe.
- Causal relationship to the IMP: related (with sub-categories: possible, probable/likely, certain), not related (with sub-categories: not related, unlikely), unknown (with sub-categories: conditional/unclassified, unassessable/unclassifiable, causal relationship missing).
- Outcome: recovered/resolved, recovering/resolving, not recovered/not resolved, recovered/resolved with sequelae, fatal, unknown.
- Non-IMP related countermeasures: none, newly started medication, trial discontinuation, others.
- Action taken with IMP: drug interrupted, drug withdrawn, dose not changed, not applicable, unknown.

Denominator for percentage calculation will be the number of all TEAEs for presentation of overall SOCs, and the number of TEAEs per SOC or PT respectively, for the presentation per SOC or PT, respectively.

Measures of location and variation will be calculated for:

- Duration of TEAEs.
- Time to onset of TEAE (days).

In addition, the time to onset of TEAEs will be summarized using time-to-event methods for the overall 5 most frequent TEAEs. Time will be weeks, until onset.

The following listings will be produced for all enrolled subjects:

- Deaths.
- Serious adverse events other than death.
- Adverse events leading to discontinuation from the trial.
- Adverse events leading to discontinuation from IMP.
- Adverse events leading to IMP dose decrease or interruption of IMP.
- Adverse events associated with the acute phase reaction.

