To alleviate the expected flu-like symptoms (acute phase reaction) potentially associated with the first intravenous administration of bisphosphonates, all subjects in both treatment groups must receive oral acetaminophen (paracetamol) starting from approximately 1 hour prior to the first infusion of IMP and then approximately every 6 hours for the 72-hour period after the first infusion in Treatment Period A and Treatment Period B. Commercially available doses of acetaminophen (paracetamol) can be used as available in the country where the trial is performed. However, the total dose of acetaminophen, including any other medications that contain acetaminophen, must not exceed the maximum allowed dose according to the local product information, and not more than 4 g/day, due to acetaminophen's known risks for hepatic toxicity. Non-steroidal anti-inflammatory drugs should not be used to alleviate the symptoms of the acute phase reaction due to their potential to cause acute changes in renal function, which may confound renal safety assessments.

All subjects will be provided with supplemental calcium and vitamin D, starting from Visit 1 and continuing through to the end of the trial. Calcium and vitamin D supplementation are considered standard of care for patients treated with bisphosphonates and other drugs that inhibit bone turnover. An appropriate daily supplement should be provided to subjects (recommended doses are 500 mg/day to 1000 mg/day calcium and approximately 1000 IU/day vitamin D as locally authorized); if a subject is currently taking calcium and vitamin D supplements, these may be continued without need for additional supplementation, provided levels of supplementation are

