Use of a placebo control is considered justifiable when there are no established effective treatments for a disease or condition (ICH E10). As reflected in a recent Cochrane review of interventions for CRPS, there is no consensus for optimal management of this condition and the limited number of published trials provides only low or very low quality of clinical evidence for any intervention (O'Connell et al. 2013). In the absence of a suitable active comparator, the use of a placebo control allows for blinding and randomization to control for expectations of benefits that may occur from being in the trial. The placebo group also controls for spontaneous changes in the course of the disease. The use of placebo in this trial does not imply that subjects will be untreated, as subjects may continue to receive stable analgesic regimens during the trial as well as short-acting analgesics in case of severe pain flare related to CRPS (for details, see Section 1.4.2).

Trial design limitations

The concomitant use of pain medications in this trial, which are allowed because of the severity of the condition, may affect the sensitivity of subject-reported outcomes and the ability to detect changes in pain intensity. Therefore, it is important to emphasize the need for stable treatment during the trial at least until Week 12 to optimize assessment of the primary endpoint. Any changes in pain medications must be recorded.

Second treatment course

For those subjects not experiencing sufficient efficacy after a first treatment course with IMP as assessed at Visit 11 (Week 26), a second treatment period (Treatment Period B) in subjects with persistent pain is included to allow subjects previously on neridronic acid and on placebo to be treated with neridronic acid either for the second or the first time, respectively. The second treatment course is scheduled to occur after 26 weeks.

Subjects treated during Treatment Period B will provide data on safety and tolerability of a second treatment course as well as descriptive data on the efficacy of a second treatment course in subjects with no or insufficient response to the first treatment course as well as in subjects who lost response to the initial treatment course. Furthermore, subjects from the placebo group can receive verum treatment in Treatment Period B.

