11.1.4.1 Visit 11 (Day 183 [Week 26]; +7 days)

Visit 11 must not occur prior to Day 183, to ensure a full 6 months of follow-up for all subjects.

If Visit 11 is not performed on Day 183, Visit 12 to Visit 15 should proceed in accordance with the originally scheduled time windows relative to Visit 11.

The following evaluations will be performed for all subjects:

- Record physical examination outcome (change from Visit 8).
- Record body weight.
- Record vital signs.
- Record concomitant medications and therapies.
- Assess further need of concomitant treatment for CRPS (in particular opioids), including decreases in dose or frequency as applicable.
- Record adverse events.
- Take blood for safety laboratory testing.
- Collect urine for quantitative urinalysis at the central laboratory.
- Perform dipstick urinalysis.
- Compliance assessment for electronic diary.
- Check trial discontinuation criteria (for details, see Section 9.3.1).
- Ask the subject to record the average, worst, and current pain on the tablet computer at the site.
- Measure edema, DMA, PPT, and AROM.
- Ask the subject to complete the EQ-5D-5L.
- Ask the subject to complete the PROMIS-29 profile and the PROMIS-EDDEP39 (the investigator should review the subject's answer to the PROMIS EDDEP39 question before the subject leaves the site and in case of suicidal ideation the investigator should consider involvement of a mental health professional).

-
- Ask the subject to complete the 6 neuropathic questions of the SF-MPQ-2.
 - Ask the subject to complete the PCS.
 - Ask the subject to complete the PSEQ.
 - Ask the subject to complete the PGI-S.
 - Ask the subject to complete the WPAI: CRPS (US sites only).
 - Collect information for medical resources utilization and health economics (US sites only).
 - Take blood for sIL-2R testing.
 - Take blood for omics testing.
 - Ask the subject to complete the PGIC.
 - Check the criteria to continue into Treatment Period B.

Decision to go into Treatment Period B

Compliance with the criteria to continue into Treatment Period B must be confirmed before allocation to IMP. The pain intensity question (question number 29, GLOBAL07) of the PROMIS-29 profile has to have a value of at least 4 at Visit 11. Subjects who do not meet the criteria to continue into Treatment Period B will continue with the Follow-up Period 2.

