**8.2.2 Further definitions**

Baseline	
Baseline is defined as the last observation (scheduled or unscheduled) before first IMP administration if not otherwise specified. In general, baseline is the value recorded at Visit 2.
 
More precisely, for post-baseline comparisons of all parameters except pain intensity in the eDiary, the assessment before first IMP administration at Visit 2 (Day 1) will serve as the baseline based on recorded date/times. In case the value planned on Day 1 is missing or in case there are multiple values before first IMP administration on Day 1, the last scheduled or unscheduled non-missing value before first IMP administration will be used.
 
For current, average, and worst pain, baseline pain intensity will be calculated as the average of the non-missing pain intensity ratings obtained over the 7-day baseline pain assessment phase prior to first IMP administration.

Investigational Medicinal Products (IMP)	The IMPs used in this trial are neridronic acid and matching placebo.
On-treatment-period	For the purpose of this trial, the on-treatment period starts at the first IMP administration (included) and continues until the date (included) when the subject leaves the trial, i.e., at the Final Visit (Visit 17, week 52 after Follow up period 2) for trial completers, and otherwise at the End of Trial date for subjects not fully completing the trial. The on-treatment period extends beyond the dosing period. This is because of the persistence in bone and potentially prolonged effect of neridronic acid.
Pooling of sites	Individual sites will be pooled by geographic region. Geographic regions are defined as USA/Canada, Europe, and Other Regions (including Asia-Pacific and Australia/New Zealand).
Pre-treatment-period	Before the first IMP administration (excluded).
Treatment Period A completers	
Treatment Period A completers are treated subjects who completed IMP administration in Treatment Period A according to the protocol, i.e., subjects who received the full dose of all 4 planned infusions.
 
Subjects are identified via the “Treatment Period A completer” page in the CRF based on the data point “Did the subject complete the treatment?”

Follow-up Period 1 completers	Follow-up Period 1 completers are treated subjects who completed the Follow-up Period according to the protocol, i.e., subjects who have a Visit 11 not before Day 183. Subjects do not need to be Treatment A completers.

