**Time to onset of adverse events**

Time to onset of adverse events will be calculated based on the first administration of IMP based on the imputed value for adverse event start date/time.

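### The symptom window for acute phase reaction runs from the first IMP intake, placebo included, so symptoms after a Treatment Period B infusion cannot be classed as acute phase reaction

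*SAP*

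**What the plan says.** SAP 15.1.2 sets two rules for acute phase reaction. The dedicated PT has no time limit: "Adverse events associated with acute phase reaction include the PT Acute Phase Reaction in all cases". Twelve symptom PTs are added, "but only if occurring in the first 3 days after 1st IMP intake and not lasting longer than 3 days".

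The SAP does not define first IMP intake separately. SAP 8.2.2 states: "The IMPs used in this trial are neridronic acid and matching placebo". The same section opens the on-treatment period at the first IMP administration and runs it to the end of the trial. SAP 19.1.6.1 uses the same anchor for onset: "Time to onset of adverse events will be calculated based on the first administration of IMP". Nothing restarts the clock at Visit 11.

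On the design, Protocol 11.1.4.1 says "Visit 11 must not occur prior to Day 183", and Protocol 8.1 says "subjects from the placebo group can receive verum treatment in Treatment Period B". Protocol 8.2 places the reaction typically after the first administration, with little or none after later ones. Protocol 1.4.2 requires acetaminophen around the first infusion and then "for the 72-hour period after the first infusion in Treatment Period A and Treatment Period B".

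**The concern.** For a subject who starts on placebo, the first IMP intake is the placebo infusion on Day 1. If that subject enters Treatment Period B, the first aminobisphosphonate exposure comes about six months later, and that is when Protocol 8.2 would expect the reaction. The rule can class a headache after the placebo infusion as acute phase reaction, but not fever after the same subject's first neridronic acid infusion.

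For initial-neridronic-acid subjects who are retreated, the symptom-based count in Period B is zero by construction. The summary therefore cannot show whether the reaction is weaker on second exposure.

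This matters because Protocol 8.2 names the reaction as the most common side effect of the class when given parenterally, and Protocol 8.1 gives safety of a second course as a purpose of Period B. The exempt PT is only a partial safeguard. Protocol 6.3 reports arthralgia, fever and headache as the most frequent events in the earlier 400 mg trial, and these correspond to PTs that are subject to the window. Capture in Period B would depend on whether the investigator recorded a diagnosis or symptoms.

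**Working it through.** The plan states no figure on this point, so there is none to reproduce. The check has a date part, which needs no assumption, and an illustration of size, which does.

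**Dates**

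- The first IMP intake is at Visit 2, Day 1 (SAP 8.2.2; SAP 19.1.1.4). A 3-day window from Day 1 ends at the latest on Day 1 + 3 = Day 4.
- Visit 11, the first Period B infusion, is on Day 183 with a window of +7 days, so Day 183 to Day 190 (Protocol 1.7.2).
- The gap is 183 − 1 = 182 days at least and 190 − 1 = 189 days at most.

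No symptom after a Period B infusion can start inside the window. The number of symptom PT events in Period B that can be classed as acute phase reaction is 0, whatever the initial treatment.

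**Exposures outside the window**

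There are 90 subjects planned per arm (SAP 5.2). Let f be the share of initial-placebo subjects treated in Period B. The documents give no value; f = 0.3 to 0.8 is an assumption.

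- f = 0.3: 0.3 × 90 = 27 first active exposures.
- f = 0.8: 0.8 × 90 = 72 first active exposures.

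These are exposures, not reactions. With an assumed symptom-based reaction rate r of 10% to 50%, subjects with unclassified reactions would number from 27 × 0.10 = 2.7 (about 3) to 72 × 0.50 = 36.

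**Pooled crude rate**

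SAP 15.1 plans a pooled group of everyone who received neridronic acid. SAP 15.1.2 defines the crude incidence rate as subjects with the event divided by N in the group. Assume that r is the same at first active exposure in both arms, that second-course reactions add no new subjects, that symptoms after the Day 1 placebo infusion are not counted in the pooled numerator, and that the display covers events from both phases. Then:

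- true rate = r(90 + 90f) / (90 + 90f) = r
- rate under the rule = 90r / (90 + 90f) = r / (1 + f)

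| f | pooled N | rule rate ÷ true rate |
|---|---|---|
| 0.3 | 117 | 90 / 117 = 0.77 |
| 0.5 | 135 | 90 / 135 = 0.67 |
| 0.8 | 162 | 90 / 162 = 0.56 |

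For example, r = 30% and f = 0.5 give 27 / 135 = 20% instead of 30%. If the pooled display were instead limited to events starting in Period B or Follow-up Period 2, the symptom-based rate would be 0 by the date check.

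**The case against.** - **The anchor may be per period.** The SAP does not say that first IMP intake means first in the whole trial. The protocol does use first infusion per period, in 1.4.2 and in footnote m of 1.7.2. That reading is possible. It is the weaker one, because the SAP's own anchors run from Visit 2 without a restart, and two readings that give different tables would still need a sentence to choose between them.
- **The events are not lost.** This stands. Period B symptoms remain TEAEs and appear in the general tables by PT and System Organ Class, with intensity and causality. Safety analyses are descriptive (SAP 15), and no confirmatory result is involved. The comparison of arms after the Day 1 infusion uses the same window in both arms and is unaffected.
- **The dilution is conditional.** This stands. SAP 15.1.2 also relates percentages to the totals shown in the table, and under that rule unaffected subjects need not enter the denominator. Only the crude rate is diluted. Further, SAP 15.1.1 promises trial-phase display for the overview tables, which have no acute phase reaction row, and SAP 15.1.2 does not say that the acute phase reaction summary is shown by phase or for the pooled group.
- **Prophylaxis in both periods proves little.** It is also consistent with initial allocation staying blinded, and it does not show that the protocol expects an equal reaction on second exposure. The argument for initial-placebo subjects rests on Protocol 8.2, not on the prophylaxis.

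A reader might infer that acute phase reaction is missed for every initial-placebo subject, or that 27 to 72 reactions go uncounted. The documents support neither. The dedicated PT counts whenever it occurs, only subjects who meet the Visit 11 criteria (Protocol 1.3.3) enter Period B, and 27 to 72 counts exposures.

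**Conclusion.** The point holds for the 12 symptom PTs. Read with the SAP's own definitions, the rule excludes every one of these symptoms after a Period B infusion, including those at first neridronic acid exposure in initial-placebo subjects treated in Period B. The acute phase reaction summary and listing are therefore incomplete for Period B. Because SAP 15 puts all safety data up to the cut-off into the 26-week report, both that report and the final one can be affected.

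The exclusion itself follows from dates alone. Its size rests on assumptions: 27 to 72 first active exposures if 30% to 80% of 90 placebo subjects are retreated, and a pooled symptom-based crude rate at about 77% to 56% of its true value, if such a rate is shown across both phases and reaction rates are equal at first exposure. This is a misclassification in one safety grouping. It is not a loss of adverse event data and does not bear on efficacy.

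**What to change.** In SAP 15.1.2, anchor the onset condition for the symptom PTs to within 3 days after the first infusion of each treatment period. Leave the duration limit and the unrestricted rule for the PT Acute Phase Reaction as they are.

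State that the acute phase reaction summary uses the trial-phase display of SAP 15.1 and the four treatment groups of SAP 8.1. First and second exposure can then be read separately. No new grouping is needed, since both displays are already defined, and the listing follows from the same flag.

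Cost: one SAP sentence and one programming flag, with no new data collection.
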